sera per fibrosis category and diagnostic group (total= 40 patients). In addition to simple across-group and across-category comparisons (ANOVA), correlations between the degree of fibrosis (biopsy scores) and individual biomarker peak intensities will be analyzed by Spearman rank-order correlation. Analyses according to fibrosis stage will be made overall and stratified by HCV-HIV co-infection status. Individual biomarkers that make unusually large contributions to the CART algorithms generated will be targeted for identification at this stage. We will focus on optimal samples for discovery and validation work. Once candidate biomarkers have been validated and identified, we will test intentionally ‘mishandled’ (e.g., repeated freeze-thaw) to assess the robustness of the each biomarker.

SELDI Data Analysis–Validation Larger numbers of sera will be separated by fibrosis category: minimal fibrosis (F0-1), mild fibrosis (F2), moderate fibrosis (F3), severe fibrosis/cirrhosis (F4) to assess the discriminatory ability of the individual biomarkers or biomarker patterns (n = 50-100 per fibrosis category and infection group). Ideally, equal numbers of patients will be studied in each of these groups. Although it may be more difficult to recruit individuals at the extremes (F0-1, F4), we observed the following distribution of fibrosis scores: 13 (28%) with F0-F1; 14 (35%) with F2, 10 (22%) with F3 and 9 (20%) with F4 among the 46 patients evaluated in our APRI validation study[47]. These data suggest that we should have a fair distribution across stages of fibrosis. If we find that scores are not evenly distributed, we may regroup stages to achieve groups of comparable sizes for analysis. The intensities of individual biomarker peaks and biomarker profiles will be compared within and between mono-infected and co-infected subjects as outlined above. All biomarkers making important contributions to distinguishing between groups and/or fibrosis categories will be confirmed by MALDI TOF MS and identified using a range of immunologic and mass spectrometric techniques (e.g.: EIAs when commercial kits exist or can be built easily, immunoprecipitation, Edmond sequencing, MS/MS).

Data abstraction To assess the contribution of various clinical and biologic data on laboratory markers at the time of serum sampling, data will be abstracted from the CCC database and from the clinical database of HCV mono-infected subjects studied. These values will include but are not limited to demographic and treatment data, HCV genotype, quantitative HCV RNA, ALT, AST, platelet count, INR, total bilirubin, albumin and for HIV infected patients, plasma HIV RNA, CD4 cell count.

Justification for sample size Much of the published protein profiling work does not meet minimal standards for sample size. Although sample size considerations are critical, the process of defining ‘adequate’ can be difficult when no prior knowledge exists about the proteins under study. While standard sample size calculations can be applied, none works particularly well in the context of proteomic profiling because so little is known *a priori* about the complexity of the final model before an experiment is completed, or about the individual biomarkers that will be included in that model.[89, 90] This is why biomarker studies are typically divided into three phases. In **Phase 1 (Discovery)**, small numbers of specimens (~10 cases/controls) are subjected to extensive fractionation across multiple chip chemistries and conditions to optimize the detection of discriminatory proteins/peptides. In this phase, the focus is on sensitivity and stringency is typically low. **Phase 2 (Validation)** concentrates on confirmation and consolidation of findings from Phase 1 using much larger numbers of samples to test whether proteins are differentially expressed for each candidate biomarker individually and in various combinations. Sample size estimates depend on the sample variance and desired detectable difference in expression. In previous proteomic studies on HCV-associated HCC described above, mean mass to charge ratios (m/z) of individual proteins detected ranged from approximately 3-25 with standard deviations of 1.3-14.[86, 87] The vast majority, however, have ranged between 2-5 with standard deviations of 2-4. Thus, at the lower range of variance, a sample size of 30 per group would provide 80% power to detect a 1.5-fold difference in protein expression with $\alpha < 0.05$. At the higher range of variance, 113 samples per group would be required to provide the same level of power. These estimates are in keeping with the experience of Drs [name] & [name] and from the wider clinical proteomics literature. In general, 50-100 specimens are required to estimate sensitivity and generate initial specificity estimates in clinical proteomics experiments. In the context of our study, we have planned to study 50-100 subjects per fibrosis stage, in both mono-infected and co-infected subjects (200-400 total

samples). It is in **Phase 3** studies that findings can be further validated through extensive analysis with other sample sets or control groups in addition to protein/peptide identification.

Feasibility Of 424 patients currently enrolled in the CCC, 53% are on HAART (with HIV RNA<50 copies/ml and CD4> 350) of whom 20% have undergone liver biopsy. Thus, we presently have sufficient samples to conduct Phase 1 studies in the co-infected. The full cohort is actively recruiting and is expected to reach its target by December 2008. Extrapolating from the currently enrolled patients, we expect 150-200 eligible subjects available for study. HCV mono-infected will be recruited retrospectively (through database review) and prospectively through the RVH HCV clinics which perform on average \approx 175 biopsies/yr. Thus the number of samples we require represents about 40% of available patients.

General Data Analyses Assessment parameters for the accuracy of proteomic biomarkers for the detection of significant hepatic fibrosis and cirrhosis will be calculated as shown in the simplified example in the table below. SAS PROC LOGISTIC (V.8.02; SAS Institute, Cary, NC) will be used to calculate AUROCs. Standard errors for the AUROC will be calculated according to Hanley and McNeil.[91] Primary analyses will group HIV co-infected and mono-infected subjects together according to level of fibrosis. We will also calculate the parameters for HIV co-infected and mono-infected separately. In addition, we will analyze promising candidate biomarkers combined with other markers of fibrosis that we are studying in parallel ongoing projects (e.g. HA, SHATA, APRI etc.).

Table 1. Diagnostic characteristics comparing proteomic biomarkers with liver biopsy scores

		Stage of HCV on Liver Biopsy	
		No Fibrosis/No Cirrhosis	Significant Fibrosis/cirrhosis
Proteomic biomarker	+	a (true positive)	b (false positive)
	-	c (false negative)	d (true negative)

Sensitivity = $a/a+c$; Specificity = $d/b+d$; Positive predictive value = $a/a+b$; Negative predictive value = $d/c+d$

IX. ROLES OF THE INVESTIGATORS

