2. To validate these biomarkers and calculate the sensitivity, specificity, positive and negative predictive values for the detection of significant hepatic fibrosis compared to liver biopsy (the current gold standard).
3. To compare proteomic profiles in HIV-HCV co-infected and HCV mono-infected controls at similar fibrosis stages to determine if protein profiles are expressed differently.
4. To compare serum biomarkers with ongoing immunologic and non-invasive marker studies.

VI. METHODS

We will use a variety of methods to identify candidate biomarkers that could be 1) predictive of hepatic fibrosis, 2) sensitive to change over time and with exposure to therapeutic interventions, such as HAART, and HCV therapy and 3) potentially informative about the pathogenesis of HCV disease, particularly in the setting of HIV infection. The current proposal forms one of the key elements in a broader research program aimed at identifying markers of fibrosis. Concurrent projects will evaluate immunologic, serologic and radiologic markers (and are/will be funded separately). The novel aspect of the current proposal is the serum proteomics biomarker discovery effort that will be conducted in collaboration with Drs. [name] and [name].

Our overall approach for biomarker discovery will proceed step-wise with selection of well-defined controls at each step (Fig. 1). As multiple aliquots of serum and plasma are made at each patient visit, we will be able to evaluate each candidate biomarker in parallel, permitting comparative analyses and assessment of their utility alone and in combination. Furthermore, as PBMC aliquots are similarly stored, comparisons can be made with ongoing immunologic studies at the same time points.

Figure 1. Proposed overall schema for discovery and validation of potential biomarkers.

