Biomarker Discovery for HIV–HCV Most biomarker programs focus on a single disease. Our attempt to define serum biomarkers associated with progression of liver disease in HIV–HCV co-infection is quite novel. However, it will likely be complicated by the intrinsic variability of the two underlying conditions and the varied therapeutic interventions used. Although the SELDI TOF MS platform is ideally suited to this type of complex situation, we will still need to exercise great care in selecting both patients and controls (see below). The stages of any biomarker program are Discovery, Validation and Identification. We will approach this complex problem in three general Phases.

Phase 1: Our initial **Discovery** effort will focus on otherwise ‘healthy’ HCV mono-infected controls and HIV-HCV co-infected patients with preserved CD4 cell counts (>350 cell/ul) and suppressed HIV RNA (< 50 copies/ml for at least 6 months on stable HIV treatment). Both groups will have evidence of replicating HCV (RT-PCR RNA+). Patients with other causes of liver disease or co-morbidities (i.e., current alcohol or drug use, Hepatitis B, TB) or prior/current HCV treatment will be excluded. This strategy should minimize potential “noise” in the serum proteome arising due to HIV-related immunosuppression and comorbidities (see detailed patient selection methods below).

Phase 2: Validation studies will be conducted with the groups above but in greater numbers (50-100 per fibrosis category) to confirm the validity of candidate biomarkers and guide prioritization efforts for biomarker **Identification** (see Sample Size Justification below). As samples accrue in our CIHR-funded archive, we will also have the opportunity to apply SELDI analysis to small numbers of serial samples from individual patients (e.g., with repeated biopsies). These sample sets may provide further validation of candidate biomarkers and/or biomarker patterns.

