Rationale for the selection of controls As we are primarily interested in studying biomarkers specific for HCV-related liver fibrosis progression, HIV negative, HCV+ controls are important. Although we do not collect samples on HIV negative persons as part of the cohort study, we have established close collaborations with the HCV clinics at the Royal Victoria Hospital (RVH) [see attached Letters from Collaborators]. These clinics serve a large population of HCV mono-infected patients and perform approximately 175 liver biopsies annually. We will prospectively recruit control subjects from these clinics. We have chosen not to include an HCV negative, HIV+ control group initially. Since our primary interest is liver disease and subjects with HIV mono-infection do not routinely undergo liver biopsy (our gold standard tool), we will not initially include an HIV-only group. However, we acknowledge that we may need suitable HIV+ controls in the more advanced phases of this biomarker discovery program as we attempt to tease out the effects of the interactions between HIV and the host from HCV on biomarker expression. Similarly, we will not study HCV negative, HIV negative controls with other liver diseases given that our primary focus is the discovery of biomarkers to distinguish between stages of liver fibrosis in the setting of HCV rather than differentiate HCV related fibrosis from other causes. Some of this latter work is, in fact, being carried out by others (see below).

Proteomics Discovery Program Proteomics as applied to human health research is the direct measurement of the proteome in biological fluids in different disease states. Proteomic studies of chronic HCV infection may permit the detection of proteins produced directly by the virus or of host proteins or peptides uniquely produced and/or processed in the presence of HCV, collectively referred to as biomarkers. Both individual biomarkers and biomarker patterns have the potential for diagnostic and prognostic applications in human health.

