This proposal is an example of the type of translational research that can be developed from a population-based cohort study. It provides for a synergistic collaboration between two investigators, combining expertise in clinical study design and statistics with serum proteomic methods. It will serve as an excellent training opportunity for a new generation of HIV-HCV researchers. As discussed above, a major challenge in proteomic studies is that heterogeneity among subjects and the presence of confounding variables can lead to artifacts in the assignment of a phenotypic response to the disease process under study. Failure to consider variations in sample collection, storage and quality can further compromise the ability to identify protein profiles that correspond to specific histologic phenotypes.[92] Thus, the clear advantage to our study is our ability to select samples from a population that is extremely well-characterized, having instituted strict patient selection criteria and rigorous sample collection and storage procedures. We have presented a step-wise discovery program. Phase 2 studies are obviously dependent on success in Phase 1. A growing body of literature supports that the population proteomics approach will be fruitful for studying fibrosis in HCV.[83, 85-88] Indeed, our studies in mono-infected subjects will serve to confirm (refute) work published in this area to date, as well as extend it by identifying all of the candidate biomarkers. Our own pilot data support our ability to detect potential biomarkers that can distinguish advanced fibrosis from minimal to no fibrosis in HIV-HCV co-infection using the techniques we are proposing. We already have sufficient samples to perform Phase 1 studies among HIV-HCV co-infected persons. Our current data support our ability to recruit enough patients for study once the full CCC has been enrolled. Although a considerable number of HCV mono-infected controls must be recruited, we are confident that we can do this rapidly for Phase 1 studies. Given the large number patients evaluated annually in the clinics (n=175), we do not anticipate difficulties in recruiting sufficient controls for Phase 2. However, if recruitment is lower than anticipated, we will extend recruitment to other centres. For example, several CCC co-investigators (e.g., [name], [name], [name]; see collaborators list) run large HCV mono-infection clinics. The advantages and disadvantages of the SELDI platform have been discussed in detail above. Although we have based our primary discovery program on SELDI, we do not intend to rely on a single platform for these studies. The recent acquisition of a high-throughput TOF/TOF by Drs [name] & [name] further mitigates against both the real and perceived limitations of SELDI.

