APPENDIX 4.**HIV-HCV Cohort Site Recruitment Statistics**

Clinic Site	Total HCV pts followed	Number expected to recruit	Number Recruited to Date (Feb 2008)	% With biopsy
MCI	150	120	131	16
MGH	120	80	45	10
NDH/ CHUM	140	100	130	15
QL/EM	200	150	11	10
Ottawa	300	150	20	20
Toronto	87	60	24	52
Hamilton	100	50	0	60
Calgary	143	100	37	12
Vancouver	350	150	20	5
Halifax	57	50	2	10
Windsor	30	20	4	5
TOTAL	1677	1030	424	20

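### In Phases 1 and 2 infection group coincides with HAART and, under the base plan, with the source of the sera, so an Aim 3 difference cannot be attributed to HIV-HCV biology

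*Protocol*

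**What the plan says.** - **Aim.** Specific Aim 3 (section V) is "To compare proteomic profiles in HIV-HCV co-infected and HCV mono-infected controls at similar fibrosis stages to determine if protein profiles are expressed differently". Hypothesis 2 (section II) expects such differences to reflect the faster fibrosis of co-infection.
- **Treatment.** Under Phase 1 (section VI, Biomarker Discovery for HIV–HCV) co-infected patients must have "suppressed HIV RNA (< 50 copies/ml for at least 6 months on stable HIV treatment"). For Phase 2, "Validation studies will be conducted with the groups above but in greater numbers (50-100 per fibrosis category"). HAART exposure is examined in Phase 3, while the proposal concentrates on Phases 1 and 2. An HIV-only group is left out at first (section VI, Rationale for the selection of controls).
- **Source.** Co-infected sera are selected from the CCC database and archive (section VIII, Patient Selection), which draws on 13 sites (section IV). The cohort holds no samples from HIV-negative people. Of the RVH clinics the control rationale says "We will prospectively recruit control subjects from these clinics". The Feasibility paragraph says controls are found both retrospectively, by database review, and prospectively, again through RVH. Section XI, Strengths and Limitations, brings in other centres, including mono-infection clinics run by CCC co-investigators, only if recruitment falls short.
- **Timing.** Feasibility states that enough co-infected samples for Phase 1 are already in hand. Section XI, Study Timelines, still has the control consent forms, ethics submission and sample database to prepare. It has both groups recruiting for Phase 2 in year 2.
- **Handling.** Sera are frozen at –80°C, never thawed and taken within a year of biopsy, and spectra are read blind (section VIII). Robustness comes last: "Once candidate biomarkers have been validated and identified, we will test intentionally" mishandled sera. Strengths and Limitations itself warns: "Failure to consider variations in sample collection, storage and quality can further compromise the ability to identify protein profiles".

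**The concern.** Aim 3 compares two groups that differ in more than HIV. All of one group takes HAART and none of the other does. One group's sera come from a multi-site archive, the other's from one hospital's clinics. In Phase 1 one set is already in the freezer and the other has still to be drawn. A peak that responds to a drug, to processing or to storage would show the same group difference as a peak that responds to co-infection.

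At stake is the reading of Aim 3 and Hypothesis 2. Such a peak could be reported as a clue to accelerated fibrosis and carried into confirmation and protein identification. Larger Phase 2 numbers make this more likely, because they sharpen the estimate of the mixed effect without separating its parts.

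**Working it through.** **1. The plan's own sample size.** Justification for sample size gives 30 and 113 per group for 80% power to detect a 1.5-fold difference, with SDs of 2 to 4. Assume a baseline mean of 3 (inside the stated 2–5), so the difference is 1.5. Then n = 2 × (1.96 + 0.84)² × (SD/1.5)².
- SD 2: n = 28 (29 with the t-distribution), against 30 stated.
- SD 4: n = 112 (113 with the t-distribution), against 113 stated.

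The figures reproduce. In SD units the target difference is 1.5/2 = 0.75 and 1.5/4 = 0.375. The calculation asks only whether a difference is detected, not what causes it.

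**2. Can the effects be separated?** Code each subject by intercept, fibrosis category, HIV, HAART and source (CCC or RVH). Under the base plan the last three columns are identical: 1 for every co-infected subject and 0 for every control. The matrix has rank 3 of 5, so no regression, stratification or matching within these data can divide the effect.

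If some controls came from CCC centres, the rank rises to 4. Source becomes estimable, but HAART remains the same column as HIV. With 200 per group and a share f of controls at CCC centres, the variance of the HIV contrast adjusted for source, relative to unadjusted, is (1/200 + 1/(200f)) / (2/200) = (1 + 1/f)/2:
- f = 0.10: 5.5
- f = 0.25: 2.5
- f = 0.50: 1.5

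**3. How often would a non-HIV shift look like a finding?** Let HIV have no effect and let HAART, source or handling shift a peak by b SD. The documents give no value for b, so a range is shown. Two-sided 0.05, normal approximation: P = Φ(b√(n/2) − 1.96) + Φ(−b√(n/2) − 1.96).

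| n per group | Where it arises | b = 0.25 | b = 0.3 | b = 0.5 |
|---|---|---|---|---|
| 20 | Phase 1, both fibrosis categories | 0.12 | 0.16 | 0.35 |
| 50 | One stage, lower Phase 2 number | 0.24 | 0.32 | 0.71 |
| 100 | One stage, upper number; or half of 200 in total | 0.42 | 0.56 | 0.94 |
| 200 | Four stages × 50; or half of 400 in total | 0.71 | 0.85 | >0.99 |

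Example: b = 0.3, n = 100 gives 0.3 × √50 = 2.12 and Φ(0.16) = 0.56. With no shift the figure would be 0.05. For scale, 0.3 SD is 0.3/0.375 = 80% of the plan's smaller target difference and 0.3/0.75 = 40% of the larger.

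**4. Does the infection-by-stage interaction escape this?** A shift equal at all stages cancels from it, but so does an HIV effect equal at all stages. In a balanced 2×2 layout with N subjects the main effect has variance 4σ²/N. The difference of differences has 4 × σ²/(N/4) = 16σ²/N, four times as much.

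**The case against.** Several points on the other side stand.

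- **Disclosed and staged.** The restriction to treated, suppressed patients is there to reduce noise. HAART is assigned to Phase 3, and the protocol explains the missing HIV-only group (no routine biopsy) and accepts that one may be needed later. So this is not an oversight. But deferring the question does not limit what Aim 3 will claim from Phases 1 and 2.
- **Safeguards.** Never-thawed sera, the one-year window, central coding and blinded spectra are sound. They prevent thaw damage and operator bias. They do not equalise processing or storage duration between two collections, and the pilot degradation check covered eight co-infected sera only.
- **Unseen material.** The sample-handling figure (Appendix 1) is not shown, and a protocol for the mono-infected patients was still to be written. A common procedure may be set there, so its absence from this text is weak evidence.
- **The mishandling test.** It was meant to probe the robustness of finished markers, and freeze-thaw is its only named example. Discovery sera are already chosen to exclude that stress.

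Some stronger readings are tempting, but the documents do not support them:

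- *Sample age is aliased with group throughout.* It is separated in Phase 1. In Phase 2 both groups recruit in parallel, so storage time may differ but overlaps. The documents also disagree on whether control recruitment is prospective only or partly retrospective.
- *No centre can supply both groups.* The Appendix 4 table, "HIV-HCV Cohort Site Recruitment Statistics", covers 11 of 13 sites, mostly as unexpanded abbreviations, so a link between RVH and a cohort site cannot be excluded.
- *Aim 3 should become an interaction test.* That changes its question and costs precision (step 4).
- *The fibrosis findings are compromised.* The primary analysis groups patients by fibrosis level and is repeated within each infection group. Contrasts within a group do not depend on the split in source.

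**Conclusion.** The point holds for Aim 3 and Hypothesis 2. In Phases 1 and 2, HIV and HAART are inseparable by eligibility, and source is inseparable from both unless the recruitment contingency happens to be used. Storage time adds to this in Phase 1. A difference between groups at the same stage is therefore a difference between treated co-infected and mono-infected patients from different collections.

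The size rests on an assumed shift. At 0.3 SD the chance of a nominally significant difference without any HIV effect is about 0.32, 0.56 and 0.85 at 50, 100 and 200 per group, for a single peak at 0.05. The comparison at one stage, which is what Aim 3 describes, corresponds to the 50 and 100 figures; 200 applies when stages are pooled. Whether any given peak shifts this much is unknown. The separability result needs no such assumption. It rests only on the eligibility rule and on the stated sources.

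**What to change.** 1. **Align the sera.** Collect and process mono-infected sera under the CCC procedure, and choose co-infected sera of similar storage time. Where a centre can supply both groups, including the co-investigators' clinics now held as fallback, use it and compare within centre as a sensitivity analysis. State one account of control recruitment, since the control rationale and Feasibility differ. Cost: some extra work in sample selection and earlier ethics submissions at any added clinic. A small share of shared-centre controls gives an imprecise adjusted contrast (step 2).
2. **Move the mishandling test forward.** Run it on a few pooled sera in Phase 1 and flag peaks that move before Phase 2 selection and identification. Freeze-thaw is already planned, so this part is only a change of order. Processing delay and storage duration are the likelier differences between sources; testing them would be a small addition.
3. **Limit the Aim 3 conclusion.** State that main-effect differences in Phases 1 and 2 are between treated co-infected and mono-infected patients, not separable from HAART, nor from source where no centre supplies both groups. Report the infection-by-stage interaction as a supplementary contrast, not as a replacement for Aim 3. Cost: wording, and a narrower claim.

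None of this separates HAART from HIV. That remains for the Phase 3 groups the protocol already foresees.

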Patient Selection To address our first hypothesis, primary analyses will focus on identifying biomarkers associated with fibrosis that are present in both HCV+ and HIV/HCV-co-infected persons. The gold standard for comparison will be the grade of fibrosis assessed on liver biopsy using the Batt and Ludwig scoring system. In this classification, those with minimal portal fibrosis or no fibrosis are scored as F0-F1, periportal fibrosis as F2, bridging fibrosis as F3 and cirrhosis as F4. In order to facilitate recruitment of appropriate subjects, the database of the CCC will be queried. Individuals having undergone a liver biopsy and who have stored serum samples within one year of the biopsy will be selected for study. We will use the fibrosis scores provided by the local site pathologist to select subjects. Standard semi-quantitative scores are used at all centres. The reports from all biopsies performed will be converted to the Batt and Ludwig scoring system for the purposes of analyses [see attached Histologic Grading of Liver Biopsies; APPENDIX 3]. In order to validate the biopsy readings, which may vary due to the expertise of the local pathologist, biopsy slides for all subjects in Phase 1 will be re-read by a single pathologist experienced in liver histology at the McGill University Health Centre. This pathologist will read all biopsies blinded to co-infection status, clinical and proteomic data. HCV mono-infected controls undergoing liver biopsy as part of routine care will be recruited through the RVH Hepatology and Infectious Diseases HCV clinics. Serum samples within one year of liver biopsy will be obtained after informed consent and stored frozen until analyzed.

SELDI Data Analysis-Discovery Previously frozen (–80°C) but never thawed serum samples within one year of liver biopsy will be studied initially. In order to ensure blinding in the SELDI analyses, samples will be aliquoted and coded in [name] laboratory and sent to [name] where SELDI spectra will be collected without knowledge of the fibrosis stage or diagnostic group. Discovery studies (Phase 1) will focus on HIV co-infected and HCV mono-infected groups at the extremes of the range of fibrosis (i.e., advanced fibrosis/cirrhosis (F>3) vs. minimal fibrosis (<F2)). Initially, we will study 10

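### Co-infected sera from up to 13 sites are selected and compared by fibrosis stage without regard to site, so site handling differences could pass for stage differences; the risk is plausible, not shown, and cheap to control

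*Protocol*

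**What the plan says.** Under Patient Selection (section VIII), co-infected subjects are found by querying the cohort database: "Individuals having undergone a liver biopsy and who have stored serum samples within one year of the biopsy will be selected for study". Stage for selection is read locally: "We will use the fibrosis scores provided by the local site pathologist to select subjects". Section VI adds clinical criteria (CD4 count, HIV RNA, no co-morbidity, no HCV treatment). None of these refers to site.

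Under SELDI Data Analysis-Discovery, Phase 1 compares "advanced fibrosis/cirrhosis (F>3) vs. minimal fibrosis (<F2"). The size is "Initially, we will study 10" "sera per fibrosis category and diagnostic group (total= 40 patients"). Phase 2 plans 50-100 per fibrosis category and infection group.

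On analysis, the Discovery text says "Analyses according to fibrosis stage will be made overall and stratified by HCV-HIV co-infection status", and General Data Analyses says "Primary analyses will group HIV co-infected and mono-infected subjects together according to level of fibrosis". Site is not mentioned in either place.

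Section IV puts the cohort at 13 sites. Appendix 4 lists 11, with the percentage biopsied at each. Mono-infected controls come from the clinics of one hospital; other centres are a contingency (section XI, Strengths and Limitations).

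The protocol recognises the hazard in general terms. Section VI counts control of sample handling among the critical elements of a biomarker programme, and section XI warns: "Failure to consider variations in sample collection, storage and quality can further compromise the ability to identify protein profiles".

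**The concern.** In a multi-site serum bank, site is where differences in collection, processing time and storage would arise. A peak sensitive to handling will differ between stage groups if two conditions hold together: handling differs by site, and the stage groups draw on the sites in different proportions.

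Uneven biopsy rates make the second condition conceivable. A site that biopsies half of its patients may include many with little fibrosis, while one that biopsies one in twenty may biopsy selected patients. The protocol does not say whether this is so.

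If both conditions hold, the error is a bias, not noise. It does not shrink with sample size, and the same cohort sites supply Phase 2. A co-infected comparison could then confirm the artefact. At stake are mainly the markers thought to be peculiar to co-infection (Hypothesis 2, Aim 3): an artefact confined to cohort sera would look like one.

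**Working it through.** **The plan's own figure.** 10 sera × 2 fibrosis categories × 2 infection groups = 40, as stated. The co-infected stage comparison is therefore 10 against 10.

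**Where biopsied patients come from.** Multiply recruits to February 2008 by percentage biopsied (Appendix 4):

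| Site | Recruits × % | Biopsied | Share |
|---|---|---|---|
| MCI | 131 × 16% | 21.0 | 31% |
| NDH/CHUM | 130 × 15% | 19.5 | 29% |
| Toronto | 24 × 52% | 12.5 | 18% |
| MGH | 45 × 10% | 4.5 | 7% |
| Calgary | 37 × 12% | 4.4 | 6% |
| Ottawa | 20 × 20% | 4.0 | 6% |
| QL/EM, Vancouver, Windsor, Halifax | 11 × 10%, 20 × 5%, 4 × 5%, 2 × 10% | 2.5 | 4% |
| Hamilton | 0 × 60% | 0 | 0% |
| All | 424 | 68.4 | |

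Toronto holds 24/424 = 6% of recruits but 18% of the implied biopsied pool. At the expected recruitment of 1030, the pool is 173.9, and Toronto (31.2) plus Hamilton (30.0) supply 61.2/173.9 = 35%. Scaled to 950 patients it is 173.9 × 950/1030 = 160. Applying the printed percentages to recruits is an assumption: it gives 68.4/424 = 16%, against a printed total of 20%, and one percentage belongs to a site with no recruits.

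**How a bias would arise.** For a peak with no true stage effect, the expected difference between stage groups is Σ over sites of (site's share of F4 sera − its share of F0-1 sera) × site shift. It is zero if either the shares or the shifts are equal.

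*Single-site illustration (shares and shift assumed).* One site supplies 40% of one stage group and 10% of the other, and shifts the peak by 1 SD.
- Bias = (0.40 − 0.10) × 1 = 0.30 SD.
- Average variance = 1 + (0.40 × 0.60 + 0.10 × 0.90)/2 = 1.165, so SD = 1.08.
- At 50 per group, 0.30/(1.08 × √(2/50)) = 1.39, and P(Z > 1.96 − 1.39) is about 28%.
- Simulation of the unadjusted two-sided 5% t-test gives 9%, 28% and 50% at 10, 50 and 100 per group. With equal shares (18% each) it stays near 5%.

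*All-site illustration (link and variance shares assumed).* Sites are weighted by the expected biopsied counts at 950. Site carries 10-50% of a peak's variance. The F4 share runs from about 7% at the highest-biopsy site to about 41% at the lowest, with the F0-1 share moving the other way. Rejection of a null peak, F4 against F0-1, co-infected sera only:

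| Stage-site link | 10 per stage | 50 per stage |
|---|---|---|
| None | 5% | 5% |
| Moderate (7% to 41%) | about 6-8% | about 7-18% |
| Strong (4% to 57%) | 6-12% | 11-29% |

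A site term in the model brings every case back to about 5%.

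**Effect on the other analyses.** In a similar model (F4 share 11% to 53% across sites), mono-infected sera carry no site effect. The pooled test then rejects in about 5% of cases at 10 per stage and 6-12% at 50. A significant difference in the same direction in both infection groups occurs in well under 1%.

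**Chance imbalance.** With no stage-site link at all, two random groups of 10 from the current pool still differ in site mix by 0.38 on average (total variation distance). That adds noise, not systematic bias.

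**Whether Phase 1 could be paired by site.** The Feasibility figures give 424 × 53% × 20% = 45 eligible patients. With the stage counts of the APRI validation study, 45 × 9/46 is about 9 with F4 and 45 × 13/46 is about 13 with F0-1. Ten of each are needed.

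**The case against.** The strongest reply is that both links are assumed. Appendix 4 reports how often sites biopsy, not what the biopsies show, and nothing in the protocol indicates that handling differs by site. Without either link, the test holds its 5% level. This stands in full. A reader might infer from the biopsy range that stage is confounded with site; the documents do not support that.

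The range also overstates the present contrast. The 60% site had no recruits, the two 5% sites contribute about 1.2 of 68 biopsied patients, and two sites with nearly equal rates (16% and 15%) supply 59%. This stands for the current pool, less so at full recruitment.

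The primary hypothesis asks for markers present in both infection groups, and an artefact of cohort sites cannot produce a stage difference in single-hospital controls. This stands too, so it would be wrong to infer that validation is powerless against such artefacts in general. It does not protect markers sought in co-infection alone, and protects the pooled analysis only in part.

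The other safeguards do less. Coding and blinding prevent operator bias, the single-pathologist re-read corrects stage and covers Phase 1, and never-thawed −80°C storage fixes one handling variable. Careful procedures are asserted but not documented by site. The test on deliberately mishandled sera does address handling, but only after candidates have been validated and identified. None of these balances site across stages.

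The Phase 2 figure at 50 per stage uses the protocol's target. A pool of 160 would hold only about 160 × 9/46 = 31 with F4, so the co-infected inflation at attainable numbers would be somewhat smaller.

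Finally, a site term may be left to the analysis plan. Which sera are drawn may not: if the stage groups come largely from different sites, no later model can separate the two.

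**Conclusion.** The point holds as a plausible and avoidable risk. The protocol fixes selection and comparison by stage with no reference to site, although it names handling variation as a threat. Under a moderate assumed link between site and stage, with site carrying 10-50% of a peak's variance, the false-positive rate in the co-infected comparison is about 6-8% at 10 per stage and about 7-18% at 50. With no link it is 5%. Phase 1, a low-stringency screen by design, is therefore little affected, and the matter is chiefly one for Phase 2 and for co-infection-specific markers. These figures show what could happen; they do not estimate what will. Confidence that a bias is actually present is low. The change is still worth making, because the data that would settle the question are held by the cohort and the remedy costs little.

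**What to change.** - **Before drawing co-infected sera:** tabulate fibrosis stage by site, and frequency-balance F4 and F0-1 across sites as far as the available numbers allow. Strict pairing within site should not be required, since only about 9 F4 and 13 F0-1 patients appear eligible now.
- **Phase 2, co-infected comparisons:** use a site-stratified test, or a site term in the ANOVA and logistic models with small sites pooled. Flag any candidate whose stage effect disappears within site.
- **Reporting:** give the site-by-stage table with the results.

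The cost is slightly less freedom in choosing sera and a few degrees of freedom in Phase 2. The 10 per cell and the total of 40 in Phase 1 are unchanged, as are the Phase 2 targets.
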